9. RESEARCH DESIGN AND METHODS

This trial is designed as a pilot study to determine the range and mechanism of monitoring biochemical surrogates of rosacea after daily topical Ivermectin 1% cream treatment. This is a single-site 16-week open label study at University of California, San Diego. Up to 25 subjects (age 18+) with at least one inflammatory papule (IGA>1) and at least mild erythema (see Clinical Assessment for Inclusion Criteria) will all be treated with topical ivermectin daily for up to 12 weeks with 4 in-office visits (screening, then monthly follow-ups for 3 months and one follow-up telephone visit one month after study medication completion). Twenty tape strip samples (similar to the tape strip method described in Dyjack, et. al. 2018) from each of the four sites will be obtained at each visit to determine KLK activity and LL-37 expression and/or up to twelve skin swabs to assess skin microbiome. Safety monitoring has been established based on both the most likely reactions and the most serious though extremely rare events. At each visit, in addition to one planned phone call, the subject will be queried tolerance of therapy and Adverse Events. The study will end with the last subject completing the telephone visit (Visit 5/week 16). If a patient does not return for a follow up visit after baseline, a replacement patient will be added.

The biochemical analysis of protease activity and LL-37 cathelicidin expression obtained by tape strip analysis at each time point and compared to baseline. Analysis of the tape strips will compare baseline to week 12 and also be correlated to the trends assessed in the tape strip analysis. The skin microbiome obtained by skin swab will also be analyzed at each time point and compared to baseline.

Ivermectin 1% cream is lawfully marketed in the U.S. as a topical treatment for inflammatory lesions of rosacea. Subjects will be instructed on the proper application of Ivermectin topical cream in accordance with the package insert, and they will apply a pea-sized amount for each area of the face that is affected daily. This research proposal therefore does not involve a route of administration, dose, or patient population that significantly affects the risk to benefit ratio associated with the use of the drug product.
Furthermore, this is a proof of concept study, and therefore, this investigation is not intended to support a

change in advertising of the drug, in labeling, nor in promoting the drug product.

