On Visit 3, rosacea severity will again be evaluated. Tape strips and/or skin swabs will be collected from the same sites as in the initial collection. Patients will be instructed not to apply the study drug on the morning before the tape strip samples are collected on return visits. Study drug will be weighed, and additional drug will be provided as needed. The total time for this visit will be approximately 1 hour.

VISIT 4 Week 12 (+/- 4 days)

On Visit 4, rosacea severity will again be evaluated. Tape strips and/or skin swabs will be collected from the same sites as in the initial collection. Patients will be instructed not to apply the study drug on the morning before the tape strip samples are collected on return visits. Study drug will be weighed, and additional drug will be provided as needed. The total time for this visit will be approximately 1 hour.

Visit 5 Week 16 (+/- 4 days) (phone follow-up)

Subjects will be contacted via phone to inquire about any adverse events experienced since the last in clinic visit. This phone call will take approximately 5 minutes.

Clinical assessments for inclusionary criteria:

IGA scale, a subjective 5-point measure of overall disease severity. IGA scores range from 0 to 4: 0 = no signs or symptoms present (clear); 1 = 1 to 2 small, noninflammatory papules (near clear); 2 = 3 to 10 papules/pustules (mild); 3 = 11 to 19 papules/ pustules (moderate); and 4 = 20 or more papules/pustules and nodules (severe).

Erythema scale: Scores range from 0-4: 0=none (no redness present); 1= mild (slight pinkness); 2= moderate (definite redness); 3=significant (marked erythema); and 4=severe (fiery redness). For inclusion criteria subjects will require at least mild erythema.

Lesional site identification and sample collection:

At Visit 1, Four ~20x20mm areas will be identified as clinically involved. These sites will be recorded to ensure subsequent sampling is from the same area during follow up visits (Visits 2-4).

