Standard Tape stripping-Four sites will be selected, ideally two on the right cheek, and two on the left cheek. Commercially available stratum corneum sampling tape (such as D-Squame) will be used for 20 repeated tapings. To ensure consistent sampling methods, a pressure instrument (D500-D-squame® pressure instrument, CuDerm, Dallas, TX, USA) will be applied to the tape of the tape strip for uniform pressure. The tape is placed on the skin and removed and placed into an Eppendorf tube. This will be repeated 20 times. Tape stripping is a well-accepted less invasive method in dermatologic research that is now becoming an alternative to skin biopsy for certain assays. As we are doing here, we hope to validate this sampling method for use in larger studies and transition its use into clinical practice. In summary, 20 tape strips from each of the four sites, for a total of 80 tape strips will be collected at each visit for biochemical evaluation. They will be stored at -80°C until processing.

Standard Skin Swabs

Skin swabs will be done to collect bacteria from participants' skin. Swabs are then analyzed for the amount of bacteria and the presence of different bacterial species picked up by the swab. After swabbing, the swab are placed into either an empty Eppendorf tube (if analyzing the DNA of the bacteria present on the skin surface) or into a liquid medium such as tryptic soy broth (if analyzing the amount of bacteria present on the swabbed skin surface). These tubes are then stored at -80 degrees Celsius until analyzed for the data previously mentioned. The exact location of all swabbings, including whether the swabbing was taken from lesional or non-lesional skin in a patient with an inflammatory skin condition, will be recorded in the participant's file.

Laboratory Assessments

Processing of Tape-strips:

The tape strips from the same visit from the same patient will be combined and processed together. Tapes will be immersed in 1 ml of 10mM Tris-HCl (ph 7.8) + 0.1% TritonX and vortexed. Protein extracts will be completely lyophilized and the pellet dissolved in 40 μ l of PBS pH 7.4.

Cathelicidin LL-37 protein analysis (tape strips)

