For quantification of cathelicidin, 2 μ l of each sample or serially diluted synthetic LL-37 peptide as a standard will be dotted onto a nitrocellulose membrane. The membrane will be blocked with 5% non-fat dry milk in PBS for 1 h, incubated overnight with rabbit antibody to LL-37 at 4°C followed by incubation for 1 h with HRP-conjugated goat antibody to rabbit IgG. The immunoreactions will be visualized by Western Lighting chemiluminescence reagent plus and the density of each blot measured with NIH Image and compared with standard controls. Alternatively, SELDI-TOF-MS (surface enhanced laser desorption ionization, time of flight, mass spectrometry) can be used to determine the cathelicidin peptide size. These procedures are developed in our laboratory to determine cathelicidin peptides from skin tape strip samples. Since the recovery of material from tape stripping may be variable, not all patients may have sufficient material for these studies.

Skin Swabs

Samples will be analysed for the bacterial composition of the skin either by amplicon sequencing utilizing 16s ribosomal RNA amplification, quantitative polymerase chain reaction (qPCR), whole genome shotgun metagenomics or other next generation sequencing method.

Statistical Methods

Demographics, Population, and Baseline Characteristics

Background and baseline demographic data and subject disposition data will be tabulated and presented for all enrolled participants. Subjects will be classified by severity of disease. The background and baseline characteristics will consist of age, race, sex, past and current medical conditions, and results from the physical examination. Continuous data (i.e., age) will be summarized descriptively by mean, standard deviation, median, and range. Categorical data (i.e., sex, race, and severity of disease) will be presented as enumerations and percentages. T-test will be used to evaluate continuous data and chi-squared test for categorical data.

Primary and Secondary Analysis

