All information required will be entered into the Case Report Forms (CRFs). The objective of this trial is to determine if 12 weeks of topical ivermectin to affected areas of facial skin can decrease biochemical markers of rosacea-specific inflammation and affect the skin microbiome. Changes in lab measures before and after treatment will be compared pre and post Ivermectin treatment using paired sample t-tests. Variables with right-skewed distributions will be log transformed at each time (pre and post treatment) before analysis. If log transformations do not provide distributions suitable for 2-sample t-tests (based on violation to the normality assumption), the Wilcoxon Rank-Sum test will be employed.

Sample Size Calculation

Given this is a proof of concept study, no sample size calculation will be performed.

Safety Data

All AEs, including SAEs, occurring during the course of this study will be listed for all subjects. Adverse events resulting in discontinuation from the study will be listed separately. Other information collected about AEs (e.g., severity or relationship to study procedures) will be listed as appropriate.

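### The nonparametric fallback for the pre/post lab measures is the Wilcoxon rank-sum test, an independent-samples test, although every comparison is within subject

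*Combined protocol and SAP*

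**What the plan says.** The rule is in Section 9, under Statistical Methods, Primary and Secondary Analysis. It has three steps.

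1. Main test: "Changes in lab measures before and after treatment will be compared pre and post Ivermectin treatment using paired sample t-tests".
2. Transformation: "Variables with right-skewed distributions will be log transformed at each time (pre and post treatment) before analysis".
3. Fallback, if the logs do not yield "distributions suitable for 2-sample t-tests (based on violation to the normality assumption), the Wilcoxon Rank-Sum test will be employed".

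The rest of Section 9 fixes the data structure. There is a single group, whose members "will all be treated with topical ivermectin daily for up to 12 weeks". At each return visit, "Tape strips and/or skin swabs will be collected from the same sites as in the initial collection". For the biochemical assays, "The tape strips from the same visit from the same patient will be combined and processed together". Each subject therefore contributes one tape-strip value per visit, and the pre/post pair is formed by subject, not by site.

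No signed-rank test, paired permutation test or other paired nonparametric method appears in the document.

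**The concern.** Step 1 is a paired analysis; step 3 is not. The rank-sum test compares two independent samples and takes no account of which post-treatment value belongs to which baseline value. Here there are no two independent samples to compare.

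The wording of step 3 raises a second problem. A paired t-test relies on approximate normality of the within-subject differences. The plan does not say that the differences are examined. It refers to two-sample t-tests and to transforming at each time, which suggests that the separate pre and post distributions would be inspected. Those can be non-normal when the differences are well behaved, so a measure could be moved off a valid paired t-test and onto the wrong fallback.

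What is at stake is Aim 1, whether 12 weeks of treatment changes the inflammatory markers or the microbiome. With at most 25 subjects and no sample size calculation, there is little information to spare.

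**Working it through.** **Inputs.** From the documents: up to 25 subjects, one arm, one pooled tape-strip value per subject per visit, baseline compared with later visits. The plan states no power figure to reproduce. Assumed here: two-sided 5% level; pre/post correlation ρ of 0, 0.3, 0.5 or 0.7; a true shift of 0, 0.5 or 1.0 SD; complete pairs.

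**Why correlation matters.** In SD units, the mean pre/post difference has true standard error SE = √(2(1−ρ)/n). An unpaired test behaves as if it were √(2/n). Treating the rank-sum test as approximately a two-sample comparison:

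- true size = 2[1 − Φ(1.96/√(1−ρ))]
- paired power = Φ(0.5/SE − 1.96)
- unpaired power on paired data = Φ((0.5 − 1.96√(2/n))/SE)

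With n = 25 and ρ = 0.5, SE = √(1/25) = 0.200 and √(2/25) = 0.283. Then:

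- size = 2[1 − Φ(2.77)] = 0.6%
- paired power = Φ(2.50 − 1.96) = Φ(0.54) = 71%
- unpaired power = Φ((0.5 − 0.554)/0.200) = Φ(−0.27) = 39%

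| ρ | SE | True size, unpaired | Power, unpaired | Power, paired |
|---|---|---|---|---|
| 0 | 0.283 | 5.0% | 42% | 42% |
| 0.3 | 0.237 | 1.9% | 41% | 56% |
| 0.5 | 0.200 | 0.6% | 39% | 71% |
| 0.7 | 0.155 | 0.03% | 36% | 90% |

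**Simulation of the two rank tests.** 40,000 trials per scenario; rank-sum by normal approximation with continuity correction, signed-rank exact. Data were bivariate normal, or bivariate t with 3 df scaled to unit SD. A separate run of 20,000 trials agreed to within about 1 percentage point.

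True size of rank-sum at n = 25 (normal data): 2.1%, 0.8% and 0.1% at ρ = 0.3, 0.5 and 0.7. Signed-rank stays at about 5%.

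Power for a 0.5 SD shift, rank-sum vs signed-rank:

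| ρ | n = 25, normal | n = 25, t(3) | n = 15, normal | n = 15, t(3) |
|---|---|---|---|---|
| 0.3 | 37% vs 51% | 67% vs 76% | 20% vs 31% | 41% vs 52% |
| 0.5 | 34% vs 64% | 68% vs 87% | 18% vs 42% | 40% vs 64% |
| 0.7 | 33% vs 86% | 72% vs 97% | 14% vs 62% | 40% vs 82% |

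At ρ = 0 and n = 25 there is no loss: 38% vs 38% (normal), 64% vs 62% (t). The n = 15 columns matter because the plan warns: "Since the recovery of material from tape stripping may be variable, not all patients may have sufficient material for these studies".

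For a 1.0 SD shift at n = 25 the relative loss is at most 3%. At n = 15 with normal data it is larger: 75% vs 84%, 78% vs 94% and 83% vs 99% at ρ = 0.3, 0.5 and 0.7, a relative loss of 11% to 17%.

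**Where normality is judged.** 4,000 trials, n = 25, 0.5 SD shift, with a skewed (exponential) between-subject component and normal within-subject error, so that the differences are exactly normal. A 5% Shapiro-Wilk test on the separate pre and post values triggers the fallback in 18%, 31% and 52% of trials at ρ = 0.3, 0.5 and 0.7. Applied to the differences, it triggers in about 5%. In the triggered trials, power is 39% vs 50%, 41% vs 68% and 45% vs 87% (rank-sum vs the paired t-test that was abandoned).

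**The case against.** The text is not in dispute, but four points bear on how much weight it deserves.

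- **It may be a slip.** Paired intent is explicit two sentences earlier, and a careful analyst might read signed-rank for rank-sum. However, the two-sample wording and the rank-sum test stand in the same sentence, and both describe an unpaired analysis. An analyst who follows the plan literally runs the wrong test, and a slip needs the same correction.
- **The normal-data figures overstate the typical loss.** Truly normal differences would fail a 5% Shapiro-Wilk test only about 5% of the time, so they should rarely reach the fallback. This stands: the heavy-tailed columns are the more relevant ones, and their loss at n = 25 is smaller. Even those do not condition on the fallback being triggered; a Shapiro-Wilk test on the differences rejects in only about 40% of such trials.
- **Absolute power depends on assumptions.** Without rescaling the t distribution to unit SD, the ρ = 0.5 comparison at n = 25 is 21% vs 45% instead of 68% vs 87%. The direction and the existence of a material gap do not change.
- **This is a proof-of-concept study and the error is conservative.** True, and it limits the severity. It does not justify a test that contradicts the design.

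A further caution: the plan does not state where normality is judged, so the diversion from a valid paired t-test is a possible reading, not an established fact.

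**Conclusion.** The concern holds. The fallback as written is an independent-samples test on paired data, and it contradicts the main test in the same paragraph.

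Under positive pre/post correlation the consequence is lost power. With 25 pairs and a 0.5 SD shift, the loss runs from 9 points (67% vs 76%, ρ = 0.3) to 25 points (72% vs 97%, ρ = 0.7) for scaled heavy-tailed data, and from 14 to 53 points for normal data. It vanishes at zero correlation and is small for a 1.0 SD shift at n = 25, though not at n = 15 with normal data. Correlation, shift, distribution and alpha are all assumed, since the documents give none of them.

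The scope is limited to measures still judged non-normal after log transformation, and the documents do not indicate how many that will be. The paired t-test is sound wherever it is used. If normality is checked at each time point, however, it may be set aside when it should not be. This should be corrected before analysis; it is not a threat to the study as a whole.

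**What to change.** Replace the fallback sentence with text such as:

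> Normality will be assessed on the within-subject differences (on the log scale where used). If it is not tenable, the Wilcoxon signed-rank test on the paired differences will be used, with the Hodges-Lehmann estimate of the median change (pseudomedian) and its 95% confidence interval.

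The Hodges-Lehmann estimate equals the median change only when the differences are roughly symmetric, hence the label. The same edit could usefully state how zero differences and ties are treated, since low-abundance taxa could produce them, and that a subject lacking material at either visit drops out of that comparison.

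Cost: a sentence or two of analysis text. No new data, subjects or procedures.

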10. HUMAN SUBJECTS

Up to 25 adult subjects (age 18+) will be enrolled with a diagnosis of rosacea and at least mild erythema and one inflammatory papule. The specific criteria for subjects will be discussed below. Each subject must be capable of providing informed consent.

Inclusion:

- Subject is male or non-pregnant female, 18+years of age.
- Subjects willing and able to give informed consent.
- Subjects willing and able to comply with the requirements of the study.
- Subject has the clinical diagnosis of rosacea with at least one inflammatory papule and at least mild erythema.
- Subject has been on a stable dose for greater than 3 months of medications for treatment of concurrent medical condition (including oral contraceptive pills, vasodilators, adrenergic blocking agents) OR the investigator has determined that the medications are unlikely to affect the patient's rosacea and/or treatment during the study
- Subject is in general good health in the opinion of the investigator.
- .
- Exclusion: Subject has a diagnosis of Steroid Rosacea or Pyoderma Faciale (rosacea fulminans).
- Subject has used facial topical therapies (OTC drug products or prescription products) for any reason within the prior 7 days
- Subject has used oral ivermectin within the prior 28 days.
- Subject has used systemic corticosteroid or systemic antibiotics (especially doxycycline, minocycline, tetracycline, metronidazole) within the prior 28 days.
- Subject has had laser or light-based treatment for rosacea within the prior 3 months.
- Subject has had systemic retinoids and retinoid derivatives over the past 6 months
- Subject has a known hypersensitivity or allergy to topical ivermectin or components of the vehicle.
- Subject is pregnant or lactating or planning a pregnancy during the duration of the study
- Subject has been treated with another investigational device or drug within 28 days prior to study enrollment or intends to participate in a clinical trial concurrent with this study
- Subject has clinically significant findings, medical history or conditions (other than rosacea), which in the opinion of the Investigator may compromise the study, treatment protocol, or safety of the patient or treatment allocation

11. RECRUITMENT

Patients will be recruited online through advertisements placed on Craigslist and through fliers posted around the

UCSD campus. Recruitment will be performed by investigators and study coordinators. All recruitment materials will receive approval from the IRB before utilization. Involvement will be completely voluntary (no coercion) and all risks will be clearly outlined and explained prior to enrollment. Involvement will not lead to promotion or any salary compensation.

12. INFORMED CONSENT

Informed consent is an ongoing process that includes the signing of an informed consent form. Subjects will be required to sign an informed consent form prior to being screened and before undergoing any study procedures or assessments, in accordance with ICH E6; 4.8, "Informed Consent of Trial Subjects". Subjects will be provided with a copy of the informed consent form and printed materials that explain the purpose of the study, procedures, and assessments. Subjects will also be provided with the telephone numbers of the investigator and qualified personnel who can assist with their questions and concerns. Participants will sign the informed consent form at the Outpatient Dermatology Clinic in La Jolla at the time of their screening visit prior to any study-related procedures occurring. The study procedures, as well as the risks and benefits, will be discussed with prospective participants during the recruitment process prior to scheduling their screening visit, giving participants a minimum of 2 days to consider whether or not they are interested in participating. The procedures, risk and benefits will be discussed with patients again verbally at their visit prior to providing them with and having them sign the informed consent form. Members of the research team listed below will be involved in the consenting procedure.

Please see attached consent form.

13. ALTERNATIVES TO STUDY PARTICIPATION

The alternative to participating in the study would be to not participate in the study.

14. POTENTIAL RISKS

Summary of the known and potential risks and benefits to human subjects:

Tape stripping: The risk associated with tape stripping theoretically includes only the rare possibility of allergic reaction to the tape. Since the tape is immediately removed after application, the risk of reaction is extremely low. However, in previous and ongoing studies involving tape stripping, it has been noted that a very mild erythema may develop immediately after a series of tape stripplings on one localized area of skin, presumably due to the mild mechanical disturbance. The erythema is expected to resolve within 12hrs without sequelae.

Skin swabbing: Risks from swabbing procedure during visits include discomfort and irritation during the procedure, which will promptly subside following cessation of swabbing with the cotton swab.

Risks of Medication Withdrawal: Stopping use of certain excluded medications may result in worsening of the patient's rosacea. Subjects whose rosacea will be severely exacerbated by withholding use of their normal drug regimen will be excluded.

Risk of Loss of Confidentiality: Samples will be labeled with the subject identification number prior to storage and only study investigators and study coordinators will have access to the patients' identifying information. The patients name and sample/test results will be stored separately and securely, but the principal investigator and site study staff will know which sample belongs to which patient until one year following the end of this study. At that time, the link between the subject and their sample will be destroyed and it will not be possible to determine which sample belongs to a particular patient. A patient may withdraw their sample from the study any time before the link between the patient and the sample is broken. Study participants will not be identified by name on any study documents. The study-related records will be maintained by the investigator. All study-related records (patient charts and other study records) must be retained no sooner than 2 years after data analysis is complete. Patients will be reassured that PHI will not be re-used or disclosed for other purposes.

Risks of Topical Ivermectin cream:

Although this drug was approved by the FDA for the treatment of rosacea, it does carry some risks. Hypersensitivity to topical ivermectin cream or any components of the cream is possible. Also, the study sponsor reports that the medication may cause sensations of burning/stinging/redness/itching at local sites of application. There have also been rare reports of burning, dry, itching eyes as well as redness, pain, excessive tearing or discharge, swelling of the eye if contact occurs with the eyes. This research plan does not utilize a route, dose, or patient population that differs from its lawfully marketed purpose.

Topical Ivermectin Pregnancy Category: C

There are no adequate and well-controlled studies in pregnant women.

Effect on lactation: Following oral administration, ivermectin is excreted in human milk in low concentrations; excretion following topical administration has not been evaluated

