4. ESTIMATED DURATION OF THE STUDY

2 years

5. LAY LANGUAGE SUMMARY OR SYNOPSIS (no more than one paragraph)

This study will assess the role of topical Ivermectin 1% cream and its effect on protease and antimicrobial peptide expression and on the skin microbiome (the microorganisms that live on the skin) in rosacea. This is a single-site 16-week open-label study at University of California, San Diego. We will do this by first measuring serine protease activity and cathelicidin and skin microbiome of all subjects. All subjects will receive Ivermectin topical cream and will be instructed on how to apply it daily for 12 weeks. Participants will return for monthly visits during which their clinical symptoms of facial redness and number of facial papules will be scored, and they will have repeat tape stripping and/or skin swabs. At the end of the study, tape strips and skin swabs will be analyzed to determine serine protease activity and skin microbiome of participants at each of their visits and expression of cathelicidin (LL-37) mRNA. We will then look at changes in serine protease activity and LL-37 expression and skin microbiome over time, and we will also determine whether or not these changes correlate with disease severity.

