Table of Events

Visit number	Screening /Baseline Visit 1*	2	3	4	5 (Phone Visit)
Time of Visit	Day -31 to Day 0	Week 4	Week 8	Week 12	Week 16
Demographic Information	x				
Inclusion/Exclusion criteria	x				
Informed consent	x				
Physical examination	x				
Rosacea Severity Score (IGA & CEA)	x	x	x	x	
Medical History	x				
Subject Satisfaction Assessment					
Tape strip	x	x	x	x	
Skin swabs	X	X	X	X	
Weigh/dispense study medication as needed	x	x	x	x	
Weigh and return study medication		x	x	x	
Adverse events	x	x	x	x	x

*Patients who require washout may be re-screened

VISIT 1 (Day 0)

Prior to beginning any study procedures, subjects will first be asked to review and sign the informed consent form. After obtaining informed consent, the inclusion/exclusion criteria will be reviewed. A brief medical history and physical exam will be performed in helping to assess whether the subject meets the required criteria for the study. Female subjects of child-bearing potential will complete a urine pregnancy test while in our office to ensure that they are not pregnant. Patients who meet the inclusion and exclusion criteria will then have their rosacea severity scored by two different standardized grading scales: IGA and erythema scale. At the screening visit may occur at the same time as your screening visit if none of your medications are excluded. Tape strips and/or skin swabs will be collected from 4 areas of involved rosacea facial skin. Subjects will then be given a pre-weighed tube of study medication and instructed to apply the medication daily. Subjects will also be instructed not to apply the study drug on the morning before the tape strip samples are collected on return visits. The total time for this visit will be approximately 1 hour.

VISIT 2 Week 4 (+/- 4 days)

On Visit 2, rosacea severity will again be evaluated. Tape strips and/or skin swabs will be collected from the same sites as in the initial collection. Patients will be instructed not to apply the study drug on the morning before the tape strip samples are collected on return visits. Study drug will be weighed, and additional drug will be provided as needed. The total time for this visit will be approximately 1 hour.

VISIT 3 Week 8 (+/- 4 days)

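### Baseline can follow a washout that may itself worsen rosacea, and no analysis uses washout status, so the pre/post change can mix withdrawal effects, in either direction, with any ivermectin effect

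*Combined protocol and SAP*

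**What the plan says.** **Entry after washout.** Section 10 excludes a candidate if "Subject has used facial topical therapies (OTC drug products or prescription products) for any reason within the prior 7 days", and likewise if "Subject has used systemic corticosteroid or systemic antibiotics (especially doxycycline, minocycline, tetracycline, metronidazole) within the prior 28 days". Longer look-back periods apply to light-based treatment and systemic retinoids. The footnote to the Table of Events in section 9 adds "Patients who require washout may be re-screened", and section 15 also refers to a washout period. Stopping a treatment in order to qualify is therefore an expected way into the trial.

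**Effect of stopping.** Section 14 warns: "Stopping use of certain excluded medications may result in worsening of" the patient's rosacea. Section 15 repeats the warning for the condition being treated. The next sentence of section 14 excludes subjects in whom withholding their usual regimen will cause a severe worsening. That exclusion is not in the section 10 list, and the general investigator-judgement criterion there concerns conditions apart from rosacea.

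**Baseline.** Severity scores, tape strips and swabs are taken at the screening/baseline visit, which for subjects needing washout means after it. No repeat baseline is planned, and nothing requires the rosacea to be stable first.

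**Design and analysis.** "This is a single-site 16-week open label study at University of California, San Diego"; "All subjects will receive Ivermectin topical cream and will be instructed on how to apply it daily for 12 weeks". The size is "Up to 25 subjects (age 18+) with at least one inflammatory papule". Section 9 states "Changes in lab measures before and after treatment will be compared pre and post Ivermectin treatment using paired sample t-tests", with log transformation and a rank-test fallback. It also compares each visit with baseline, and the section 5 summary adds correlation with disease severity. Prior rosacea treatment and washout status are not named as a baseline characteristic, covariate, stratum or sensitivity analysis.

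**The concern.** The protocol names a cause of altered disease at baseline, allows it in an unknown share of subjects, and then makes that baseline the only comparator for its main objective. If stopping treatment raised LL-37, protease activity or the clinical scores, and this receded during the 12 weeks, the recovery would appear as a fall on ivermectin. If earlier treatment was still suppressing the markers at baseline, its wearing off would push the change upwards and could hide a real fall. Either way, a single mean change over all subjects cannot be separated into its parts, and no control arm absorbs the difference.

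What is at stake is attribution: whether a pre/post change can be called an effect of ivermectin. The problem is more specific than the general limits of an uncontrolled design, because the trial can examine it if washout status is recorded. Status not captured at entry may be hard to recover later.

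**Working it through.** **There is no plan figure to reproduce.** Section 9 states that no sample size calculation is done. It gives no SD, effect size, alpha or sidedness. What follows is an illustration.

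**Inputs**
- From the documents: n = 25 (the maximum), one arm, paired t-test on log values.
- Assumed: two-sided alpha 0.05; SD of the log ratio (Week 12/baseline) 0.7; no ivermectin effect; each subject washed out with probability w; washout raises that subject's baseline marker f-fold; a share s of the rise, on the log scale, has settled by Week 12.

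**Formulas**
- Mean shift in log ratio = −w·s·ln f; geometric mean ratio = exp(−w·s·ln f).
- Variance of the log ratio = 0.7² + w(1−w)(s·ln f)².

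**Main case, w = 0.5, f = 1.5 (ln 1.5 = 0.405), by simulation**

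| Share settled, s | Mean shift | Ratio | t-test significant |
|---|---|---|---|
| 1 | −0.203 | 0.82 | 27% |
| 0.5 | −0.101 | 0.90 | 11% |
| 0.25 | −0.051 | 0.95 | 6% |
| 0 | 0 | 1.00 | 5% |

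Hand check at s = 1: variance = 0.49 + 0.25 × 0.164 = 0.531, so SD = 0.729. The shift in standard errors is 0.203/(0.729/5) = 1.39, and Φ(1.39 − 1.96) = 0.28, close to the simulated 27%. Fixing the number washed out at 12 of 25 gives about 24%.

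**Range with full settling (s = 1)**
- w = 0.3, f = 1.25: ratio 0.94, significant in 7%.
- w = 0.2, f = 1.5: ratio 0.92, 8%.
- w = 0.7, f = 1.5: ratio 0.75, 47%.
- w = 0.5, f = 2: ratio 0.71, 57%. The section 14 exclusion, if applied, makes large rises less likely.

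**Opposite direction.** If half the subjects had a baseline still suppressed 1.5-fold and this wore off fully, the ratio with no drug effect would be exp(+0.203) = 1.22. The same shift would offset a true fall.

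**Subjects without washout.** They carry no withdrawal shift, so a test in them alone has about 5% two-sided error from this source in every scenario. The cost is precision. The effect detectable with 80% power is about 0.59 SD at n = 25, 0.78 SD at n = 15 and 1.00 SD at n = 10. At SD 0.7 these are ratios of exp(−0.41) = 0.66, exp(−0.55) = 0.58 and exp(−0.70) = 0.50.

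**The case against.** **The settling is not in the documents.** A reader might infer that the protocol describes a temporary flare that goes away by itself. It speaks only of worsening. If stopping treatment merely unmasks the subject's untreated rosacea, and that would persist without effective therapy, the post-washout baseline is the appropriate one and there is no false fall. This stands, and it is why the table runs down to s = 0. It is also tempting to take 27% as the trial's false-positive rate. That figure needs full settling as well as three other assumed inputs.

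**Section 14 already has a safeguard.** It removes predicted severe cases. This stands in part: the criterion is undefined, lies outside the section 10 list, and leaves mild and moderate worsening.

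**The link from worsening to markers is indirect.** Section 7 contrasts rosacea with normal skin. It does not say that a worsening within one person raises LL-37 or protease activity. Whether markers follow symptoms is one of the study's own questions. This stands, so f is purely assumed.

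**Aim 2.** A reader might infer that washout manufactures the correlation between marker change and clinical change. The documents do not support that. Section 7 asks whether improvement goes with a decrease in the markers. If both fall together as disease settles, the association is real, and only its attribution to ivermectin is affected. Any induced correlation is also modest. With half washed out and full settling, it is about 0.07 (f = 1.5, clinical score shifted 0.5 SD) to 0.20 (f = 2, shifted 1 SD).

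**Proof of concept.** This excuses the missing power calculation. It does not make a cheap record of washout disproportionate, though it does argue against a formal rule on when an effect may be claimed.

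**Conclusion.** The point holds in a limited form. The documents permit washout before baseline, warn that stopping treatment may worsen rosacea, and plan pre/post comparisons in one open-label arm with no use of washout status. The pooling is inferred from the absence of any washout term or subgroup; no sentence states it. The change to Week 12 can therefore mix withdrawal effects with any ivermectin effect.

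Neither the direction nor the size of the bias can be settled from the documents, which give no washout share, size of worsening, settling rate or SD. In the main illustration, a nominal 5% error becomes 27%, 11% or 5% as settling goes from full to half to none, and with few washed-out subjects or a small rise the inflation is slight. It would be wrong to conclude that a fall in this trial must be an artefact. It could not be attributed to ivermectin with confidence unless washout status had been examined. This is an inexpensive improvement that helps whichever way the bias runs.

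**What to change.** 1. **CRF, Visit 1:** record whether a rosacea treatment was stopped to qualify, which one, and the stop date. Keep this distinct from stopping an unrelated facial product, since the 7-day topical criterion covers products used for any reason.
2. **Analysis section:** report baseline values and the baseline-to-Week-12 change by washout status, with confidence intervals, and add a sensitivity analysis in subjects who needed no washout.
3. **Interpretation:** if a fall appears only in washed-out subjects, describe it as a pre/post change and do not attribute it to ivermectin. No size threshold or formal claim rule is needed; the subsets are small and not randomised.
4. **Consistency:** reconcile the exclusion for withdrawal worsening in section 14 with the section 10 list. Which text should govern is for the investigators.

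The cost is one short CRF item (yes/no, product, stop date) and a sentence or two in the analysis section; no treatment rule changes. The downside is wider intervals: if 15 of 25 subjects needed no washout, the effect detectable in them rises from about 0.59 to about 0.78 SD.
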